# 5.1.1 Dose-limiting Toxicity

For this study, a DLT is defined as any of the following AEs that occur during the DLT evaluation period (except those that are clearly and incontrovertibly due to disease progression or extraneous causes), with severity graded according to the National Cancer Institute (NCI) Common Terminology Criteria for Adverse Events, Version 4.03 (CTCAE V4.03):

- Grade  $\geq$  3 non-hematologic toxicity, except:
  - $\circ$  Nausea, vomiting and / or diarrhea lasting  $\leq$  3 days in the once per FD and twice weekly schedules or 2 days in the thrice weekly schedule that can be medically managed
  - Worsening of pre-existing tumor pain associated with tumor lesions for which the subject is irradiated in the context of this study
- Evidence of treatment-related hepatocellular injury for > 3 days in the once per FD and twice weekly schedules and 2 days in the thrice weekly schedule, such as ≥ 5 × the upper limit of normal (ULN) of alanine aminotransferase (ALT) or aspartate aminotransferase (AST) and without any other apparent clinical causality
- Any occurrence of Hy's law (defined as aminotransferases > 3 × ULN, alkaline phosphatase < 2 × ULN, total bilirubin ≥ 2 × ULN, with no other reason to account for these abnormalities)
- Febrile neutropenia or Grade 4 neutropenia lasting for > 5 days, Grade 4 thrombocytopenia or any requirement for platelet transfusion (as defined by Grade 4 thrombocytopenia lasting for > 5 days or Grade ≥ 3 thrombocytopenia with bleeding), Grade 4 anemia that is unexplained by the underlying disease
- Any toxicity related to study treatment that causes the subject to interrupt treatment (defined as having to delay the next scheduled M3541 administration) for:
  - $\circ \geq 4$  FDs in the once per FD dosing schedule.
  - $\circ$  > 1 FD in the thrice weekly schedule
  - not to be able to be treated within 24 hours of the scheduled treatment time in the twice weekly schedule
- A related treatment-emergent adverse event (TEAE) that in the opinion of the SMC is of potential clinical significance such that further dose escalation would expose subjects to unacceptable risk.

Information on DLTs will be sent by the Sponsor or delegate to the SMC core members within 1 working day of the receipt of documented information.

Document No. CC Object No. CC

Dose escalation of M3541 will start from 50 mg orally once per FD until 1 of the following stopping rules apply:

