# 5.5 Criteria for Subject Withdrawal

#### 5.5.1 Withdrawal from Study Therapy

The subject must be withdrawn from M3541 in the event of any of the following:

- Withdrawal of consent
- Development of unacceptable toxicity
- Occurrence of progressive disease (PD) according to Response Evaluation Criteria in Solid Tumors version 1 (RECIST 1.1) or initiation of any other anticancer therapy
- Occurrence of any condition that is clinically relevant and affects the subject's safety, if discontinuation is considered necessary by the Investigator and / or Sponsor prior to treatment completion
- TEAEs that cause a treatment delay of > 3 FDs of radiotherapy.
- Occurrence of RT-related Grade ≥ 3 AEs, or any AE if discontinuation of IMP is desired or considered necessary by the Investigator and /or the subject (if applicable)
- Occurrence of pregnancy
- Use of a non-permitted concomitant drug (including any other drug with known anticancer activity unless specified otherwise in Section 6.5.2)
- Noncompliance that is deemed by the Investigator or the Sponsor to compromise subject safety or study integrity.

Planned tumor assessments will continue as scheduled if a subject does not complete the protocol defined study therapy (unless subject withdraws consent).

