#### 6.4 Noninvestigational Medicinal Products to be Used

#### 6.4.1 Radiotherapy

Radiotherapy will follow institutional guidelines with the first day of RT treatment on a Monday (FD 1). The total dose of RT is 30 Gy given in 10 daily fractions (ie, 3 Gy/FD, 5 FDs per calendar week, FD 1 to FD 10 over a 2-calendar week period). An interruption in the administration of RT will result in an interruption of M3541 for as long as the RT is interrupted (see Section 6.2.1).

All effort should be made to complete 10 FDs if possible. The formal criteria for dose modification in the study are included in Table 7. The study site will provide the Sponsor with irradiation simulation details when required.

Document No. CC Object No. CC

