#### Table 7 Dose Interruption for M3541 and Radiotherapy

	Dose Modifica	ations		
Toxicity	M3541ª	Radiotherapy b		

 
Toxicities in Radiation Field
 
Observations occurring in field of irradiation (which can't be explained by the disease or any other extraneous cause) such as mucositis, radiation dermatitis, cystitis, proctitis, nausea, vomiting, etc
 
	Grade 3 Permanently discontinue M3541. In case of liver-related transaminase increases, treatment should be permanently discontinued unless the transaminase rise is undeniably due to major tumor response. Grade 4 Permanently discontinue M3541	Temporarily interrupt RT during M3541 interruption. If interruption is longer than allowed in Section 6.2.1, RT without M3541 can be resumed at the discretion of the Investigator.		
Systemic Toxicities Considered to be Unrelated to RT, Hematologic				

 
Hematologic Toxicities: Any Grade ≥ 3 toxicity, excluding:
 
	Temporarily interrupt treatment. Resume treatment (at the same	Temporarily interrupt RT during M3541 interruption. If		

 
Neutropenia lasting for ≤ 5 days and not associated with fever
 
	dose) once severity resolves to Grade $\leq$ 1 or baseline. See	interruption is longer		

 
Isolated Grade 4 lymphocytopenia without clinical correlate
 
	Section 6.2.1 for dose delay allowances.	than allowed in Section 6.2.1, RT without M3541 can be		
Grade 3 thrombocytopenia without bleeding		resumed at the		
Any grade of anemia		discretion of the Investigator.		
Systemic Toxicities Considered to be Unrelated to RT, Hepatocellular				

 
Treatment-related hepatocellular injury for more than 3 days, such as Grade ≥ 3 ALT or AST (≥ 5 × ULN) with or without elevation of serum total bilirubin to > 2 × ULN, without initial findings of cholestasis (elevated serum alkaline phosphatase) or other apparent clinical causality.
 
	Temporarily interrupt treatment. Resume treatment (at the same dose) once severity resolves to Grade ≤ 1 or baseline. See Section 6.2.1 for dose delay allowances.	Temporarily interrupt RT during M3541 interruption. If interruption is longer than allowed in Section 6.2.1, RT without M3541 can be resumed at the discretion of the Investigator.		

CCI

	Dose Modific	ations
Toxicity	M3541ª	Radiotherapy b

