
 
Systemic Toxicities, Other
 
Nonhematologic Toxicities 
 
Any Grade ≥ 3 toxicity, excluding:
 
Diarrhea (≤ 3 days duration) following adequate and optimal therapy
 
Nausea and vomiting (≤ 3 days duration) with adequate and optimal therapy
 
Fatigue or headache (< 7 days duration) following initiation of adequate supportive care
 
Any other single laboratory values out of the normal range that have no clinical significance, and that resolve to Grade ≤ 2 with adequate measures within 7 days
 
 
 
	Temporarily interrupt treatment. Resume treatment (at the same dose) once severity resolves to Grade ≤ 1 or baseline. See Section 6.2.1 for dose delay allowances.	Temporarily interrupt RT during M3541 interruption. If interruption is longer than allowed in Section 6.2.1, RT without M3541 can be resumed at the discretion of the Investigator.

AE = adverse event; ALT = alanine aminotransferase; AST = aspartate aminotransferase; CTCAE V4.03 = Common Terminology Criteria for Adverse Events, Version 4.03; FD = fraction day; IMP = investigational medicinal product; RT = radiotherapy; ULN = upper limit of normal

Note: Severity of AEs will be graded using the CTCAE V4.03 toxicity grades.

- a As all treatments with M3541 will be given in combination with RT, an interruption in the administration of RT would lead to an interruption in treatment with M3541.
- b A maximum RT interruption of ≤ 3 FDs in total is allowed within the complete treatment period. If RT / M3541 treatment have been interrupted by more than > 3 radiotherapy days, the subject must be discontinued from M3541. All effort should be made to complete 10 FDs if possible.

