#### 7.2.6 Cardiac Assessments

A 12-lead ECG will be recorded at Screening. The ECG will be recorded after the subject has been in a supine position breathing quietly for 5 minutes and prior to any associated PK blood sampling. The ECG should be obtained using a Holter recorder. The ECG results will be used to evaluate the heart rate, atrial-ventricular conduction, QR, QT, and QTc intervals, and possible arrhythmias. All ECG and ECG extract results must be reviewed at the site by the Investigator or a medically qualified designee for clinical management of the subject.

The Investigator will judge the overall ECG interpretation as normal or abnormal. If abnormal, it will be decided if the abnormality is clinically significant or not clinically significant and the abnormality will be recorded on the eCRF. Any clinically significant ECG abnormality (cardiac assessment) will be recorded as an AE or SAE as appropriate (see Section 7.4.1 and subsections).

In presence of a Grade  $\geq$  3 QTc prolongation (QTc  $\geq$  501 ms and / or an increase with at least 60 ms over baseline, on 2 separate consecutive ECGs that cannot be explained by the underlying medical condition or concomitant therapy) the treatment with M3541 should be interrupted and the subject evaluated by a cardiologist. The IMP M3541 will be re-introduced only after recovery of QTc to  $\leq$  480 ms (Grade 1) if recovery is within 3 days and the QTc prolongation was deemed unrelated to M3541. In case of incomplete recovery (QTc between 480 and 500 ms) and in the presence of demonstrated clinical benefit to the subject, described as CR, PR, or a minor response (minor response being a regression of at least 20%), M3541 may be re-introduced if the QTc prolongation was deemed unrelated to M3541 and upon agreement with the cardiologist and in consultation with the Sponsor, and with the agreed expectation that the clinical benefit of resuming M3541 treatment with RT is greater than the potential risk.

Document No. CC

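### Section 7.2.6 and Table 7 conflict on restarting M3541 after Grade ≥ 3 QTc prolongation, and Table 7 is not aligned with the DLT definition for three other event types

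*Protocol*

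**What the plan says.** **Status of Table 7.** Protocol Section 6.4.1 states: "The formal criteria for dose modification in the study are included in Table 7". Section 6.5.5 tells investigators to manage adverse events by clinical judgment together with Table 7.

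**Content of Table 7.** The hematologic, hepatocellular and other-systemic rows share one instruction: interrupt M3541, then "Resume treatment (at the same dose) once severity resolves to Grade ≤ 1 or baseline", within the delay limits of Section 6.2.1. Section 6.2.1 plans no dose reduction within a subject. The hematologic row exempts "Any grade of anemia" from interruption. The other-systemic row exempts fatigue or headache of under 7 days "following initiation of adequate supportive care".

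**QTc.** Section 7.2.6 interrupts M3541 for Grade ≥ 3 QTc prolongation. It re-introduces the drug after recovery to 480 ms or below, which it labels Grade 1, "if recovery is within 3 days and the QTc prolongation was deemed unrelated to M3541". With incomplete recovery (480 to 500 ms), restart is possible if the event was again judged unrelated, the cardiologist agrees, the Sponsor is consulted, and the subject has a CR, a PR or a regression of at least 20%.

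**DLT definition.** Section 5.1.1 counts "Any occurrence of Hy's law" and "Grade 4 anemia that is unexplained by the underlying disease". It also counts Grade ≥ 3 non-hematologic toxicity, excepting only short, manageable nausea, vomiting or diarrhea and worsening pain in irradiated lesions. Events clearly due to progression or extraneous causes are left out.

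**Withdrawal.** Section 5.5.1 requires M3541 to stop for "Development of unacceptable toxicity", which is not defined, and for RT-related Grade ≥ 3 events. It also provides for stopping when the investigator or Sponsor finds it necessary for safety, or when the investigator or subject wants to stop because of any adverse event.

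**The concern.** A site handling a Grade ≥ 3 QTc prolongation during treatment has two rules to follow, and for an M3541-related event they give different answers. The rule that restricts restart is also the harder one to find. It sits in Section 7.2, which is introduced as describing procedures for the Screening period, whereas Table 7 is the place to which Sections 6.4.1 and 6.5.5 direct the site.

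For Hy's law, unexplained Grade 4 anemia and short Grade ≥ 3 fatigue or headache, the question is different. The Safety Monitoring Committee counts these events as dose-limiting, while the dosing table either does not call for interruption or allows a return to the same dose. If the difference is intended, the protocol does not say so.

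What is at stake is subject safety and consistent handling across up to 15 sites in a first-in-human study. Section 3.1.5 reports a half-life above 48 hours, against a predicted 8 hours, with accumulation in each subject.

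**Working it through.** There is no planned figure to reproduce. The check sets the passages side by side for the once-per-FD schedule; SAP Section 7 states that the intermittent schedules were never explored.

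**1. QTc, recovery to 480 ms or below, event judged related to M3541.**
- Section 7.2.6: no re-introduction, because the unrelatedness condition fails.
- Table 7, other-systemic row: it covers any Grade ≥ 3 non-hematologic toxicity apart from listed exclusions. QTc is not among them. Recovery to Grade 1 satisfies the restart condition, and cause is not a condition. Result: resume at the same dose.
- Neither passage refers to the other or states precedence.
- The clocks differ as well: 3 days in Section 7.2.6, against up to 3 FDs in total in Section 6.2.1 and Table 7 footnote b.

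**2. QTc, recovery to 480-500 ms, event judged unrelated.**
- Section 7.2.6: restart is possible under further conditions.
- Table 7: no restart, because by Section 7.2.6's own label this is above Grade 1 (unless baseline lay there).
- The two rules therefore differ in both directions.

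**3. Can the response condition be met from scheduled scans?**
- FD 1 is Monday, Day 1; FD 6 is Day 8; FD 10 is Day 12. A 3-FD delay moves the last dose over Days 15 and 16 to Day 17.
- The first scan is PTD 42 ± 7 days (Table 1), and PTD 1 is the day after the last dose.
- No delay: 12 + 42 = Day 54 nominally; 54 − 7 = Day 47 at the earliest.
- With a 3-FD delay: 17 + 42 = Day 59; 59 − 7 = Day 52.
- Either way the earliest scheduled scan is 42 − 7 = 35 days after the last dose.

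**4. Anemia.** Grade 4, unexplained by the underlying disease: a DLT under Section 5.1.1; no interruption under Table 7.

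**5. Grade ≥ 3 fatigue or headache under 7 days.** Not among the Section 5.1.1 exceptions, so a DLT; no interruption under Table 7 once supportive care has begun.

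**6. Hy's law.** Compare the bilirubin-elevated case in Table 7's hepatocellular row with Section 5.1.1:

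| Element | Table 7 row | Section 5.1.1 Hy's law | Table 7 case inside the definition? |
|---|---|---|---|
| Aminotransferases | ≥ 5 × ULN | > 3 × ULN | yes |
| Total bilirubin | > 2 × ULN | ≥ 2 × ULN | yes |
| Alkaline phosphatase | not elevated initially | < 2 × ULN | yes |
| Other cause | none apparent | none | yes |
| Duration | more than 3 days | any occurrence | yes |

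Each Table 7 case with raised bilirubin therefore meets the Hy's law definition, and the row allows it to resume at the same dose. The row's permanent-stop counterpart for transaminase rises appears only under radiation-field toxicities.

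**7. Ceiling on further exposure where no interruption is called for.** An event on FD k leaves at most 10 − k doses; FD 3 would leave 10 − 3 = 7. This assumes that nobody uses the discretion to stop, and for anemia a fall to Grade 4 by FD 3 after entry at hemoglobin ≥ 9 g/dL. It is an upper limit, not an expectation.

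**The case against.** The best defense has four parts.

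*Section 7.2.6 is specific and Table 7 is general.* A careful reader would let the QTc rule govern. That is a reasonable reading, but the protocol does not state it, and it calls Table 7 the formal criteria. The conflict stands, although a cross-reference would go most of the way to curing it.

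*A DLT is a counting rule, not a stopping rule.* This is right. A reader might infer that the protocol orders sites to dose through DLTs, or that four event types receive opposite dosing instructions. The documents do not support that: Section 5.1.1 prescribes no M3541 action. Only QTc sets one treatment rule against another.

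*Sites may stop anyway.* Also right. Section 5.5.1 offers more than the undefined unacceptable-toxicity ground, Section 6.5.5 keeps clinical judgment, and RT-related Grade ≥ 3 events already require withdrawal. Interruption of 4 or more FDs ends M3541. These provisions narrow the gap. They leave handling to each site and are not tied to DLT status.

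*The response-based exception does no harm.* An exception that cannot be met leads to no restart. Section 7.3 also admits imaging done for clinical need, caliper measurement of skin lesions and examination findings. So the condition is out of step with the scheduled scans, not strictly impossible.

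A reader might also add transient Grade ≥ 3 laboratory values to the list, since Table 7 exempts some of them. That does not hold. The exemption covers only values without clinical significance, and under Section 7.4.1.1 such values are ordinarily not adverse events and hence not DLTs.

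**Conclusion.** The QTc conflict is real and should be corrected. For an M3541-related Grade ≥ 3 prolongation that recovers to 480 ms or below, one section bars restart and the other allows it at the same dose. For 480-500 ms the difference runs the other way, and the response condition cannot be shown by scheduled scans until at least 35 days after the last dose.

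For unexplained Grade 4 anemia, Grade ≥ 3 fatigue or headache under 7 days, and the part of Hy's law that falls in Table 7's hepatocellular row, the finding is narrower: the DLT definition and the dosing table do not align, and the protocol does not say whether that is intended.

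A reader might infer that the primary endpoint is compromised. It is not. The endpoint is whether a subject has a DLT, and a subject with a DLT enters the DLT Analysis Set whatever the number of doses (SAP Sections 8.2 and 15.1). Dosing after a first DLT could move only the descriptive split between one DLT and at least two in SAP Section 15.1.1.

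The conclusion rests on the wording of the two documents. How many subjects had such events is not known from them.

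**What to change.** Reconcile Table 7 with Sections 5.1.1, 5.5.1 and 7.2.6:

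- State the QTc re-introduction rule once, in one place, and refer to it from Table 7.
- Bring the tumor-response condition for 480-500 ms into line with the assessments that exist during treatment.
- For Hy's law, unexplained Grade 4 anemia and Grade ≥ 3 fatigue or headache, state the M3541 action consistently with their DLT status. Where a difference between counting and dosing is intended, say so.

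The sponsor decides which clinical rules stand; this point takes no view on that.

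The cost is amendment wording, with no new procedures or data. A column in the SAP Section 15.1.1 listing giving the M3541 doses on or after DLT onset would be useful but is optional. It can be derived from the adverse event listing (DLT flag, dates, action taken) and the dated administration listing in SAP Section 13.

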# 6.5 Concomitant Medications and Therapies

All concomitant medications taken by the subject from the date of signature of informed consent through the Short-term Safety Follow-up (PTD 30), are to be recorded in the appropriate section of the eCRF, noting the name, dose, duration, and indication of each drug. For pain medication taken for pain in lesions treated with per-protocol treatment (radiotherapy + M3541), the Investigator must ensure any change in ongoing pain medication or any new pain medication (name, dose, frequency, including any change in "as needed" dosing) is reported on the appropriate concomitant medications eCRF page.

Starting at PTD 31 (start of the Mid-term Safety Follow-up), only anticancer drug treatments and any change in treatment given for treatment-related SAEs should be recorded.

Contact the Medical Monitor for any questions on concomitant or prior medications.

# 6.5.1 Permitted Medicines

Any medications (other than those excluded by the appropriate sections of the clinical study protocol) that are considered necessary for the subjects' welfare and will not interfere with the IMP may be given at the Investigator's discretion.

The following medications are permitted:

Document No. CC	
Object No. CC	

- Local, topical, or short-term (ie, < 7 days) systemic corticosteroids
- Anti-infectious drugs
- · Hematopoietic growth factors, if medically indicated

The Investigator will record all concomitant medications taken by the subject and any concomitant procedures provided to the subject during the study, from the date of signature of informed consent, in the appropriate sections of the eCRF.

Any additional concomitant therapy that becomes necessary during the study and any change to concomitant drugs must be recorded in the corresponding section of the eCRF, noting the name, dose, duration, and indication of each drug.

#### 6.5.2 Prohibited Medicines

Subjects must not have received chemotherapy, immunotherapy, biologic therapy, or any other anticancer therapy within 5 x their elimination half-life, but no longer than 15 days, before the first dose of IMP administration (6 weeks for nitrosoureas or mitomycin C). Thus, the washout period for prior anticancer therapy is defined as 5 x the elimination half-life of the relevant anticancer therapy, up to a maximum of 15 days.

These therapies are generally prohibited during the treatment period and the DLT follow-up period.

Subjects with functional neuroendocrine tumor who have progressed clinically or radiographically on octreotide or lanceotide may remain on octreotide or lanceotide for control of hormonal syndromes and still be allowed on study. Similarly, subjects under stable hormone therapy (having received hormone therapy for > 3 months) may remain on hormone therapy and are allowed in the study.

Radiotherapy (involving < 30% of bone marrow) to any other lesion is allowed at any time beyond PTD 7.

Medications or herbal supplements known to be potent inhibitors or inducers of CYP3A or P-gp, OATP or OCT or drugs mainly metabolized by CYP3A, with a narrow therapeutic index are prohibited (unless as otherwise agreed to by the Sponsor). Refer to Drug Development and Drug Interactions for a classification of in vivo inhibitors (see Appendix II).

If the administration of a prohibited concomitant drug becomes necessary during the treatment period, eg, due to AEs, the subject should be discontinued from the study treatment and complete all assessments listed under the Safety Follow-up (PTDs 15, 22, and 30) and End-of-Study visits.

#### 6.5.3 Other Interventions

The following non-drug therapies must not be administered or performed during the study (and within 28 days before the start of study treatment):

Document 1	No. CC
Object No.	CCI

- Major surgery
- Herbal remedies with immunostimulating properties (eg, mistletoe extract) or known to potentially interfere with major organ function (for example, hypericin)
- Subjects should not abuse alcohol or other drugs during the study

